1.2 Original Hypothesis

- Conduction system leads can be implanted with almost no fluoroscopy using electroanatomical mapping
- 2. Using electro-anatomical mapping will increase safety of conduction system lead implantation
- The procedure times with electro-anatomical mapping will be less than that of conventional methods using fluoroscopy

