1.3 Rational for Current Study

Currently conductions system pacing can have long fluoroscopy times when compared to conventional right ventricular pacing. This may be due to difficult cardiac anatomy, altered lead trajectory and obstacles such as entanglement, that is not readily visualised with fluoroscopy. As a result operators experience additional cumulative fluoroscopy times. Our study will devise a standardised implantation protocol using 3D electroanatomical mapping systems to reduce both fluoroscopy and procedure times.

2. Study Objectives

Primary Objective

The primary objective of this study is develop a fluoroless implant protocol of conduction system leads using 3D electroanatomical mapping.

Secondary Objective

The secondary objectives will be

- To reduce the overall procedure and fluoroscopy time with utilisation of targeted lead deployment.
- 2. Improve complication rates

3. Recruitment

A total of 75 patients will be recruited for the study

50 patients with a ventricular pacing indication (high grade atrioventricular block and symptomatic trifasicular or bifasicular block) for pacing will be recruited prospectively. The patients will be divided into two groups; 25 patients in the derivation cohort and 25 patients in the validation cohort. The derivation cohort will undergo a detailed research protocol to determine the optimised work flow and this will be applied prospectively to the validation cohort.

The success rates, procedure times, complication rates and fluoroscopy times will be assessed. The 25 patients undergoing conventional methods of conduction system pacing will be recruited as a control arm to compare these outcomes.

In summary, the 75 patients will be grouped as following; 25 patients in the derivation cohort, 25 patients in the validation cohort and 25 patients in the control arm.

4. Methodology

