The CartoMerge module will be used to expedite anatomical mapping using the MRI data collected.

- 5. The mapping catheter will be removed and an intracardiac echo (ICE) catheter, will be inserted through the femoral vein.
- 6. The conduction system pacing lead will be inserted through the axillary vein. A right atrial lead will be inserted into the right ventricular apex for back up pacing in the instance the conduction system is bumped. The basal-septum, mid-septum, high-septum and anterior walls will be paced to identify electrical markers for optimal implant sites.
- 7. The lead will be visualised on the Carto maps created.
- 8. The lead will be deployed at the predetermined target site under direct visualisation using the ICE catheter. Through direct visualisation, three key determinants can be assessed:
 - 1. Lead trajectory through the septum with the goal of achieving perpendicularity
 - Lead septum interaction and whether there is evidence of entanglement preventing lead progression.
 - Relationship between the sheath and lead that can lead to or prevent failure of lead deployment.
- 9. Once the conduction lead is secured the right atrial lead will be pulled back and secured in the right atrium.
- 10. The procedure will be completed as per standard clinical implant protocol with routine clinical follow-up thereafter:

The information from echocardiography will be corroborated with the lead-septum interaction visualised on electro-anatomical maps created on CARTO.

In this cohort of patients, the conduction system lead will initially pace the His-bundle then the left bundle in order to collect data for both methods of physiological pacing. The information collected from ICE and electro-anatomical mapping will be used to develop a streamlined workflow that will map targeted areas, where challenging implant sites will be rapidly identified (such as areas of scar), reducing the number of attempted lead deployments and visualise lead-septum interaction, apposition and progression, improving safety parameters.

At the end of the procedure, the lead position will be documented with a very short, *single fluoroscopic acquisition*. This remains integral for future comparison in the instances of lead complications and in particular lead displacement.

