4.6 Study Outcome Measures

Primary Outcome Measures

1. Success rates of conduction system lead implant (fluoroless workflow vs conventional methods)

Secondary Outcome Measures

- Procedure and fluoroscopy times of the fluoroless workflow vs current conventional methods of His-bundle and Left-bundle pacing
- Procedure and fluoroscopy times of the fluoroless workflow vs conduction system implant to current right ventricular pacing
- 3. Assess capture threshold of His-bundle and Left-bundle pacing from the fluoroless workflow vs that of conventional methods of conduction system implantation
- 4. Number of times leads deployed in the fluoroless protocol vs conventional methods of conduction system implantation
- Complication rates in the fluoroless protocol vs conventional methods of conduction system implantation:

- a. Lead implanted at the incorrect position: non-septal positions
- b. Lead displacement
- c. Lead injury
- d. Rise in threshold (late complication)
- e. Vascular injury
- f. Perforation with or without subsequent tamponade
- g. Device related infection
- h. Pneumothorax

5 Participant Entry

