6.4 Serious AEs

An SAE form should be completed and faxed to the Chief Investigator within 24 hours. However, hospitalisations for elective treatment of a pre-existing condition do not need reporting as SAEs.

All SAEs should be reported to the "name of REC when allocated" where in the opinion of the Chief Investigator, the event was:

• 'related', ie resulted from the administration of any of the research procedures; and

• 'unexpected', ie an event that is not listed in the protocol as an expected occurrence

Reports of related and unexpected SAEs should be submitted within 15 days of the Chief Investigator becoming aware of the event, using the NRES SAE form for non-IMP studies. The Chief Investigator must also notify the Sponsor of all related and unexpected SAEs.

Local investigators should report any SAEs as required by their Local Research Ethics Committee, Sponsor and/or Research & Development Office.

Contact details for reporting SAEs

[contact]

[name] email: [contact]
Please send SAE forms to: [name].
[contact] (Mon to Fri 09.00 – 17.00)

7 Assessment and Follow-up

Patients will be followed up for a 1 year period. During this time they will undergo the device interrogation and wound check at 6 weeks as part of standard clinical care. One year after device implantation, patients will undergo a device interrogation follow-up appointment. Any incidental findings that we identify during the study will be reviewed by the research team and reported to the GP and also the cardiology team normally looking after the patient.

Definition of end of Study

The end of the study will be defined as completion of the 1 year follow-up of the 75 prospectively recruited patients for the invasive aspect of the study. This will be the date of the final visit of the last participant at 1 year.

8 Statistics and data analysis

The following statistical analysis has been reviewed and approved by our statistician, [name].

Power Calculations:

25 patients would provide the ability to determine the mean time of lead implantation of 120 minutes with a precision of (as a standard error) approximately \pm 10 minutes (assuming standard deviation of 47 min)⁷

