25 patients will provide the ability to determine the percentage of a successful implant with a precision of a SE (\pm 8%) of a success rate of approximately 80% SD of implant time = SD of total procedure time / $\sqrt{2}$ = 67 / $\sqrt{2}$ =47.37 SE = SD/ $\sqrt{\text{sample size}}$ = 47.37/ $\sqrt{2}$ 5 = 9.47

Data and all appropriate documentation will be stored for a minimum of 5 years after the completion of the study, including the follow-up period.

To assess the primary outcome of the success rates of the conduction system lead implant using the fluoroless workflow developed during our study, ECG information will be collected and capture will be determined by experts.

Fluoroscopy and procedural times will be analysed with one-way ANOVA. Success rates, capture thresholds and battery life will be analysed with t-test.

9 Regulatory issues

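### Section 8 fixes a pooled-variance one-way ANOVA for fluoroscopy time, although the design does not expect equal spread across the three groups

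*Protocol*

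**What the plan says.** The analysis sentence in Protocol Section 8 reads "Fluoroscopy and procedural times will be analysed with one-way ANOVA". It names no unequal-variance version, transformation or rank method. The same paragraph gives t-tests to other outcomes.

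Section 3 sets the groups: "25 patients in the derivation cohort, 25 patients in the validation cohort and 25 patients in the control arm".

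On how much fluoroscopy each group should have:

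- Section 1.2, first hypothesis: "Conduction system leads can be implanted with almost no fluoroscopy using electroanatomical mapping".
- Section 4.1, derivation cohort: "the lead position will be documented with a very short" single acquisition. Section 4.2 applies the streamlined workflow to the validation cohort but does not repeat that statement.
- Section 1.3, conventional technique: "Currently conductions system pacing can have long fluoroscopy times when compared to conventional right ventricular pacing". It suggests difficult anatomy, altered lead trajectory and entanglement as reasons, and these differ between patients.

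Section 4.6 lists as a secondary outcome: "Procedure and fluoroscopy times of the fluoroless workflow vs current conventional methods of His-bundle and Left-bundle pacing".

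**The concern.** One-way ANOVA in its usual form estimates a single error variance from all groups and uses it for the F test and for any contrast built on it. That is sound when the groups have similar spread. Here the intervention is meant to bring fluoroscopy time close to its floor, and a variable held near zero has little room to vary. Conventional implantation keeps its patient-to-patient spread. The method named therefore conflicts with what the protocol itself expects of the data.

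Fluoroscopy time is the direct measure of the first hypothesis and a listed secondary outcome. At stake are the interval reported for the reduction against conventional implantation and the p-value of the three-group test. Procedure time shares the ANOVA sentence but is not part of this point, because the design builds in no comparable difference in spread.

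**Working it through.** **The plan's own figures.** Section 8 derives an implant-time SD of 67/√2 = 47.38 (printed as 47.37), a standard error of 47.37/√25 = 9.47 min, and a standard error for an 80% success rate of √(0.8 × 0.2/25) = 0.08. All reproduce. The only SD used in planning ("assuming standard deviation of 47 min") belongs to lead implantation time, so it says nothing about the spread of fluoroscopy time.

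**Inputs.** From the protocol: three groups of 25 and one-way ANOVA. Assumed, because the protocol gives no value: two-sided alpha of 0.05, and the ratio r = fluoroless SD / control SD, taken from 0.1 to 0.5, with r = 1 as reference. The control SD is set to 1, which loses no generality.

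**Formulas**, with r the same in both fluoroless cohorts:

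- Pooled SD = √[(r² + r² + 1)/3]
- ANOVA standard error of a difference = pooled SD × √(2/25)
- True standard error, validation versus control = √[(r² + 1)/25]

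At r = 0.1 the pooled SD is √(1.02/3) = 0.583. The ANOVA standard error is 0.583 × 0.2828 = 0.165 and the true one is √(1.01/25) = 0.201, a ratio of 0.82.

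At r = 0.5 the pooled SD is √(1.5/3) = 0.707. The ANOVA standard error is 0.200 and the true one is √(1.25/25) = 0.224, a ratio of 0.89.

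As r goes to 0 the ratio tends to √(2/3) = 0.816. Coverage is then P(|t₂₄| < t₇₂,₀.₉₇₅ × 0.816) = 88.3%.

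**Simulated error rates**, normal data, equal means, 40,000 trials per row. Coverage is one minus the type I error of the contrast.

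| r | SE ratio | Coverage, validation vs control, pooled | Same, Welch | Omnibus type I error, classical F | Same, Welch's ANOVA |
|---|---|---|---|---|---|
| 0.1 | 0.82 | 88.6% | 95.0% | 8.7% | 4.9% |
| 0.2 | 0.83 | 88.8% | 94.9% | 8.4% | 4.9% |
| 0.5 | 0.89 | 92.0% | 95.2% | 6.0% | 4.7% |
| 1 | 1.00 | 95.1% | 95.1% | 5.0% | 5.0% |

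With log-normal data (coefficient of variation 0.7), pooled coverage is 86.3% at r = 0.1 and 91.5% at r = 0.5. Welch gives 92.4% and 94.1%, which is better but not a full repair.

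**If the derivation cohort is not near zero.** Let its SD equal the control SD, with validation at 0.1. The pooled variance is (1 + 0.01 + 1)/3 = 0.67, and the ANOVA standard error is 0.819 × 0.2828 = 0.231 against a true 0.201, a ratio of 1.15. Coverage for validation versus control is 97.4%, so the interval is too wide. With derivation at 0.7 the ratio is √(0.5 × 2/25)/0.201 = 0.995, and the two effects almost cancel.

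**Effect on the conclusion.** For illustration, assume control mean 10 min, SD 7, and fluoroless mean 0.5 min, SD 0.5. The pooled SD is √[(0.25 + 0.25 + 49)/3] = 4.06. The 95% half-width for the 9.5 min difference is 2.29 min pooled and 2.90 min with Welch. The t statistics are 8.3 and 6.8, so both are decisive.

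**The case against.** Several objections have force.

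- *The premise is not equally secure for both fluoroless cohorts.* The one closing acquisition is stated for derivation only. Derivation is also the exploratory phase, with pacing at several sites and both His-bundle and left-bundle pacing, and the protocol does not say that each step is free of fluoroscopy. Section 4.5 even says that participation brings radiation beyond standard care. This stands. A reader might infer that the interval against control must be too narrow, but the documents do not support that: the direction depends on the derivation cohort's spread.
- *A reader might infer that the pooled error would hide a loss of the fluoroless property between derivation and validation.* No outcome in Section 4.6 compares those cohorts; fluoroscopy time is compared with conventional conduction system pacing and with right ventricular pacing. Harm to a comparison that is not listed cannot be charged to the plan.
- *If only validation and control enter the analysis, the problem disappears.* With 25 per group the pooled and Welch standard errors are both √[(r² + 1)/25]. This is correct. But ANOVA is named here while t-tests are named for other outcomes, and the study has three groups, so a three-group analysis is the natural reading.
- *Welch's ANOVA is also a one-way ANOVA, and details may sit in a SAP that is not shown.* This is possible. Without qualification, however, the name denotes the pooled form, and the protocol states a method instead of deferring it.
- *The conclusion would hardly change.* This is accepted, and it limits how much weight the point carries.

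**Conclusion.** The point holds in limited form. The method that Section 8 names assumes a common variance that the protocol's own aim makes unlikely. With both fluoroless SDs at 0.1 to 0.5 of control, the three-group error term gives about 88% to 92% coverage for validation versus control, and the omnibus test rejects falsely about 9% to 6% of the time. With derivation as variable as control, coverage is about 97%. Only particular mixtures of spread bring it back to nominal.

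These sizes rest on assumed SD ratios, normal data, a two-sided 5% level and a three-group analysis; the protocol supplies none of the SDs. The outcome is secondary and the primary outcome is untouched. The finding of less fluoroscopy than control would very likely stand. What would be wrong is the stated precision of the reduction and the omnibus p-value.

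**What to change.** In Section 8, separate fluoroscopy time from the ANOVA sentence and state that it will be analysed without a pooled variance. Use Welch's ANOVA across the three groups. For the Section 4.6 comparison with conventional conduction system pacing, use a Welch or bootstrap interval for the difference in means, and report medians and ranges by group. A Hodges-Lehmann shift should not be added, because it assumes distributions of equal shape, which is also doubtful here. If a SAP already specifies an unequal-variance method, only the protocol wording needs to be aligned with it.

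The cost is one sentence, with no extra patients, visits or data. The interval for the reduction against control may be wider, and with strongly skewed times Welch coverage can still fall somewhat below 95%, which is a further reason to show medians and ranges.

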9.1 Ethics approval

The Study Coordination Centre has obtained approval from the "Name of REC when allocated" and Health Research Authority (HRA). The study must also receive confirmation of capacity and capability from each participating NHS Trust before accepting participants into the study or any research activity is carried out. The study will be conducted in accordance with the recommendations for physicians involved in research on human subjects adopted by the 18th World Medical Assembly, Helsinki 1964 and later revisions.

9.2 Consent

Consent to enter the study must be sought from each participant only after a full explanation has been given, an information leaflet offered and time allowed for consideration. Signed participant consent should be obtained. The right of the participant to refuse to participate without giving reasons must be respected. After the participant has entered the study the clinician remains free to give alternative treatment to that specified in the protocol at any stage if he/she feels it is in the participant's best interest, but the reasons for doing so should be recorded. In these cases the participants remain within the study for the purposes of follow-up and data analysis. All participants are free to withdraw at any time from the protocol treatment without giving reasons and without prejudicing further treatment.

9.3 Confidentiality

The Chief Investigator will preserve the confidentiality of participants taking part in the study and is registered under the Data Protection Act.

Data will be pseudonymised.

9.4 Indemnity

Imperial College Healthcare NHS Trust holds standard NHS Hospital Indemnity and insurance cover with NHS Resolution for NHS Trusts in England, which apply to this study

9.5 Sponsor

Imperial College Healthcare NHS Trust will act as the main Sponsor for this study. Delegated responsibilities will be assigned to the NHS trusts taking part in this study.

9.6 Funding

Johnson and Johnson

Patients' transport in the form of a taxi will be provided as well as refreshments during the additional appointments for purposes of the research study. We have costed £50 for transport and £10 for refreshments per visit.

Researchers will not receive any personal payment over and above normal salary, or any other benefits or incentives, for taking part in this research.

